8.3.2. Summary Measure

 Absolute PASI scores, change from baseline and percent change from baseline in PASI scores over time • Proportion of subjects who achieve ≥50% improvement from baseline in PASI score (PASI 50), at each post-baseline visit Proportion of subjects who achieve ≥75% improvement from baseline in PASI score (PASI 75) at each post-baseline visit. If the PASI score is missing, set PASI 50 or 70 to missing.

Note: Day 85 was not assessed for 0.5mg/Kg dosing cohort (cohort 7).

8.3.3. Population of Interest

The efficacy analyses will be based on the Safety population.

8.3.4. Statistical Analyses / Methods

Details of the planned displays are provided in Appendix 9 and will be based on GSK data standards and statistical principles.

Unless otherwise specified, endpoints / variables defined in Section 8.3.1 will be summarised using descriptive statistics, graphically presented and listed. For the responder endpoints, the exact Binomial 95% CI will be calculated.

8.3.4.1. Statistical Methodology Specification

Endpoint / Variables

Change from baseline in PASI scores

Model Specification

Same MMRM model as for CFB in induration (Section 8.1.4.1)

Model Checking & Diagnostics

Same approach as in Section 8.1.4.1

Model Results Presentation

 Table/Figure of the LS means of CFB and 95% CI (by treatment and visit), as well as treatment differences and 95%CI

8.4. PLSS-related endpoints (only for PsO)

8.4.1. Endpoint / Variables

The PLSS (Psoriatic Lesion Severity Sum) score for each subject at each timepoint is derived as follows.

Data available (CC SI dataset):

For each of the 2 plaques (biopsy or index), the following data will be available:

- The location of the plaque head, face, arm, leg or trunk
- For each plaque, the intensity of 3 symptoms is assessed on a 0-4-point rating scale

- Symptoms: induration, erythema, and scaling.
 PLSS total score calculated by the investigator will be in the dataset, but the PLSS score for analysis should be derived from the raw data.
- o 0-4-point rating scale: no symptoms (0), slight (1), moderate (2), marked (3) or very marked (4).

Derivation

The PLSS total score for each of the plaques (biopsy and index) is the sum of the scores for the 3 symptoms (induration, erythema, and scaling).

8.4.2. Summary Measure

• Absolute PLSS scores, change from baseline and percent change from baseline in PLSS scores over time, for index and biopsy plaques, separately.

8.4.3. Population of Interest

The efficacy analyses will be based on the Safety population.

8.4.4. Statistical Analyses / Methods

Details of the planned displays are provided in Appendix 9 and will be based on GSK data standards and statistical principles.

Unless otherwise specified, endpoints / variables defined in Section 8.4.1 will be summarised using descriptive statistics, graphically presented and listed.

8.4.4.1. Statistical Methodology Specification

Endpoint / Variables

Change from baseline in PLSS scores for the index plaque only

Model Specification

Same MMRM model as for CFB in induration (Section 8.1.4.1)

Model Checking & Diagnostics

Same approach as in Section 8.1.4.1

Model Results Presentation

[figure not shown]
 Table/Figure of the LS means of CFB and 95% CI (by treatment and visit), as well as treatment differences and 95%CI

8.5. PGA-related endpoints (only for PsO)

8.5.1. Endpoint / Variables

The Physician Global Assessment (PGA) score for each subject at each timepoint is already in the PGA SI dataset.

A 7-point scoring system will be used to measure the severity of psoriatic lesions over the whole body:

8.5.2. Summary Measure

- PGA scores, change from baseline in PGA scores (categories treated as continuous)
- PGA responses (categorical)
- PGA responders defined as subjects achieving PGA 0/1 (clear or almost clear) and at least a 2-point improvement from baseline. This will be performed on subjects with a baseline PGA score of at least 2. Set to missing if baseline PGA is 0 or 1.

8.5.3. Population of Interest

The efficacy analyses will be based on the Safety population.

8.5.4. Statistical Analyses / Methods

Details of the planned displays are provided in Appendix 9 and will be based on GSK data standards and statistical principles.

Unless otherwise specified, endpoints / variables defined in Section 8.5.1 will be summarised using descriptive statistics, graphically presented and listed.

For the responder endpoint, the exact Binomial 95% CI will also be calculated.

9. PHARMACOKINETIC ANALYSES

GUI_51487 (4.0), effective October 2014, contains the pharmacokinetic methods to be used in non-compartmental analysis (NCA) and reporting of pharmacokinetic studies. This document should be used as a reference.

9.1. Drug Concentration Measures

Refer to Section 14.4.3.

9.2. Derived Pharmacokinetic Parameters

Pharmacokinetic parameters will be calculated by standard non-compartmental analysis according to current working practices and using the currently supported version of WinNonlin All calculations of non-compartmental parameters will be based on actual

sampling times. Pharmacokinetic parameters listed will be determined from the plasma concentration-time data, as data permits.

Parameter	Parameter Description
AUC(0-t)	Area under the concentration-time curve from time zero to the time of the last quantifiable
	concentration (C(t))
AUC(0-inf)	Area under the concentration-time curve from time zero and extrapolated to "infinity"
Cmax	Maximum observed concentration,
tmax	Time to reach Cmax,
CL	Clearance
t½	Apparent terminal half-life
tlast	Time of last quantifiable concentration

NOTES:

Additional parameters may be included as required.

9.2.1. Population of Interest

The pharmacokinetic analyses will be based on the Pharmacokinetic population, unless otherwise specified.

9.2.2. Statistical Methods

Details of the planned displays are provided in Appendix 9 and will be based on GSK data standards and statistical principles.

Unless otherwise specified, endpoints / variables defined in the section above will be summarised using descriptive statistics, graphically presented (where appropriate) and listed.

10. PHARMACODYNAMIC AND BIOMARKER ANALYSES

10.1. IHC parameters

Cells in lesional biopsies are measured by IHC. There are 3 (epidermis thickness is not IHC parameters – separate section) endpoints of interest: LAG3+, CD3+, Ki67 (SI dataset: BIOMARK).

In the dataset, perivascular infiltrates (PVI) cells are also collected:

- HV (DTH): The PVI are used to locate region of interest high power fields (HPFs) for CD3+ and Lag3+ analysis. It is not a biomarker reportable (only listing)
- o PVI is not required for PsO cohorts as regions of interest for HPFs are defined by an alternative approach.

In HV (DTH) LAG3+ and CD3+ were assessed across 3 layers (slices) of the biopsy. A layer represents a section from the lesional skin biopsy tissue. Layers 1-3 represent sections obtained by cutting into the biopsy tissue block at different depths. 10 sections were discarded between each level.

In PsO, LAG3+, CD3+, Ki67 were assessed across 1 layer. The regions of interest (HPFs) for LAG3+ and CD3+ are located in either the epidermis or the superficial dermis. For Ki67, the regions of interest (HPFs) are located in the epidermis only. Epidermal thickness is also only measured in the epidermis.

LAG3+, CD3+ and Ki67 are measured in up to 5 HPFs per layer for HV or epidermis / dermis for PsO. A minimum of 3 HPFs should be present in order for samples to be evaluated.

10.1.1. Endpoint / Variables

Parameter	Endpoint	Derivation	HV (DTH)	PsO
LAG3+	Total number of LAG3+ cells HPFs (A)	For each layer (HV) or epidemis/dermis (PsO) 1. if 5 HPFs for all subjects total # of cells (per layer for HV or epidermis/dermis for PsO) = sum of cells in all HPFs (1-5) 2. If 3 or 4 HPFs for at least one subject	Y (3 layers)	Y (epidermis and dermis)
		Total # of cells of 3/4 HPFs for all subjects = sum of HPFs 1-3, or sum of HPFs 1-4 3. If less than 3 HPFs for some subjects (i.e 0, 1 or 2 HPFs), set to missing for these subjects Note: There is only 1 layer for PsO		
	Total number of LAG3+ cells averaged across skin layers	Sum of (A) as defined above for layers 1, 2 and-3 / 3 layers Note: there will be always 3 layers per subject and timepoint	Υ	N
		Programming notes: 1. Exclude from summary tables/figures if missing (but will be included in listing and individual plots) 2. No LLQ/ULQ for these assays 3. If only some values HPF are missing, it's always in sequential order: e.g. it's not possible to have only HPF2 missing, this should be HPF5		
CD3+	Total number of CD3+ cells HPFs (B)	Same derivation as for LAG3+	Y (3 layers)	Y (epidermis and dermis)
	Total number of CD3+ cells averaged across skin layers	Same derivation as for LAG3+	Υ	N
	CD3+ (cells/mm²)	(B) as defined above / number of HPFs	N	Υ

Parameter	Endpoint	Derivation	HV (DTH)	PsO
		assessed (from 3 to 5 depending on the min number of HPFs available)		(epidermis and dermis)
Perivascular infiltrates (PV) cells		No derivation	Υ	N
Ki67	Total number of Ki67+ cells HPFs (C)	Same as for as for LAG3+ but only for epidermis	N	Y (epidermis)
	Ki67 (cells/mm²)	Same as for CD3+ (cells/mm²) (C) as defined above / number of HPFs assessed (from 3 to 5 depending on the min number of HPFs available)	N	Y (epidermis)

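### One evaluable biopsy sample with only 3 or 4 high-power fields shortens that marker's count for every subject in the same layer or compartment, discarding up to 40% of the counted fields

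*SAP*

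**What the plan says.** SAP 10.1 sets the range of fields: "LAG3+, CD3+ and Ki67 are measured in up to 5 HPFs per layer for HV or epidermis / dermis for PsO". It also sets the floor: "A minimum of 3 HPFs should be present in order for samples to be evaluated".

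SAP 10.1.1 then derives the LAG-3+ total separately for each layer (healthy volunteers, HV) or for epidermis and dermis (psoriasis, PsO), in three cases:

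- All subjects have five fields: all five are summed.
- "If 3 or 4 HPFs for at least one subject": "Total # of cells of 3/4 HPFs for all subjects = sum of HPFs 1-3, or sum of HPFs 1-4".
- Fewer than three fields: "If less than 3 HPFs for some subjects (i.e 0, 1 or 2 HPFs), set to missing for these subjects".

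The programming notes add: "If only some values HPF are missing, it's always in sequential order". The fields that go missing are thus the highest-numbered ones.

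CD3+ and Ki67 totals use the same derivation, with Ki67 only in PsO epidermis. The PsO densities for CD3+ and Ki67 divide these totals by a field count of 3 to 5 set by the smallest number available, so they inherit the same common minimum. SAP 10.1.4.1 analyses change from baseline in these quantities by ANCOVA with treatment and baseline.

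**The concern.** The endpoint is a sum, so the plan has to equalise the number of fields somehow. It does so by bringing every complete sample down to the shortest evaluable one. Counts already made on valid fields are thrown away in subjects whose samples had no problem, although SAP 10.1 accepts a three-field sample as evaluable in its own right.

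The groups are small. The DTH cohort is 6 active and 6 placebo, and each psoriasis dose has 6 active against 9 pooled placebo. Change in LAG-3+ cells is a secondary endpoint in both parts (Protocol 2, SAP 2.2). Total LAG-3+ cells and Ki67 also enter the Bayesian analysis of SAP 13, which Appendix 9 lists among the outputs for go/no-go decisions. Avoidable noise here reaches a decision.

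**Working it through.** The documents give no SD, power or precision target for these endpoints (Protocol 9.2: sample size based on feasibility), so there is no plan figure to reproduce.

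**Inputs from the documents.** Maximum 5 fields; evaluable minimum 3; DTH cohort 12 subjects x 2 biopsies = 24 samples per layer; psoriasis 27 patients x 2 biopsies = 54 samples per compartment. The SAP does not say whether the minimum is taken within or across visits; 24 and 54 assume across visits.

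**Assumed inputs.** Share *w* of the five-field endpoint variance that comes from between-field variation within a biopsy: 20%, 40%, 60%. Probability *q* that a sample is short but evaluable (3 or 4 fields): 2%, 5%, independent between samples. Samples with 0-2 fields are not counted in *q*, because they are set to missing and trigger nothing.

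**Fields discarded.** For common minimum *m*, a full sample loses (5 - m)/5: 2/5 = 40% at m = 3, 1/5 = 20% at m = 4. If exactly one of *n* samples is short, the pooled share lost is (5 - m)(n - 1) / [5(n - 1) + m]:

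| | m = 3 | m = 4 |
|---|---|---|
| PsO compartment (n = 54) | 106/268 = 39.6% | 53/269 = 19.7% |
| HV layer (n = 24) | 46/118 = 39.0% | 23/119 = 19.3% |

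The modelled HV endpoint averages three layers. If only one layer is cut to 3 fields, the loss is 2 of 15 fields, or 13%.

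**Precision.** A three-field sum is on a different scale from a five-field sum, so the comparison is made per field. Relative variance is (1 - w) + w x 5/m, and CI width follows its square root.

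| w (assumed) | Variance, m = 3 | CI width, m = 3 | Variance, m = 4 | CI width, m = 4 |
|---|---|---|---|---|
| 20% | +13% | +6% | +5% | +2% |
| 40% | +27% | +13% | +10% | +5% |
| 60% | +40% | +18% | +15% | +7% |

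As a cross-check, express a single sample's variance through the correlation between its fields: ICC + (1 - ICC)/k for k fields. The ratio of three fields to five is 1.67, 1.25, 1.11 and 1.04 at ICC 0, 0.25, 0.5 and 0.75 (assumed). The full 67% variance increase arises only if fields within a biopsy are uncorrelated.

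**Chance that the rule is triggered**, 1 - (1 - q)^n:

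- PsO compartment: 1 - 0.98^54 = 66%; 1 - 0.95^54 = 94%.
- HV layer: 1 - 0.98^24 = 38%; 1 - 0.95^24 = 71%.

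These cover a minimum of 3 or 4 together. They should not be multiplied by the m = 3 inflation as if every trigger were a three-field sample.

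**The case against.** The best defence is that the rule buys comparability. Every subject is counted over the same number of same-numbered fields. In HV the fields are located through perivascular infiltrates (SAP 10.1), and missing fields are always the last ones. If fields were numbered by density, or if sparse infiltrate leaves fewer fields to count, a sample with three fields would read high on a per-field mean. A depleting drug could produce such samples more often after dosing, and the bias would then be related to treatment. The documents neither state nor exclude this. The objection therefore stands as a reason to keep the truncated version alongside. It does not justify making truncation the main analysis, because the need for equal field numbers comes from using a sum and a mean removes it.

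It is also fair that the loss is conditional: if every evaluable sample has five fields, nothing is lost. The study tests no formal hypotheses either.

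Three stronger readings are tempting but not supported:

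- A reader might infer that a subject's value shifts between planned deliveries as later biopsies arrive. The last DTH biopsy is at 72 hours and HV results first appear at Interim 1, after the last week 4 visit. The last psoriasis biopsy is at Day 29 and PsO results first appear at the full Interim 2, after all Day 85 visits (SAP 3.1, Appendix 9). Only optional dose-escalation looks at available PD data come earlier (Protocol 5.4).
- A reader might take the CD3+ and Ki67 densities as a precedent for an untruncated mean. They divide the truncated total by the common minimum.
- A reader might infer that one thin biopsy shortens every marker and site. The rule runs per marker and per layer or compartment.

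**Conclusion.** The point holds in this limited form. For a given marker and layer or compartment, one sample with 3 fields drops fields 4-5 for everyone (40%), and one with 4 fields as the minimum drops field 5 (20%). The percentages count fields, not precision. Under the assumed variance shares, CIs widen by about 6% to 18% at a minimum of 3 and 2% to 7% at a minimum of 4, and by less in HV when only one of three layers is affected. Whether the rule is triggered depends on a short-sample rate that the documents do not give; at 2% to 5% it is more likely than not in a PsO compartment. This is an avoidable loss of information on a secondary endpoint that feeds a decision table. It does not invalidate the analysis.

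**What to change.** In SAP 10.1.1, define each endpoint as the mean count per HPF over that sample's own evaluable fields (3 to 5), and keep samples with fewer than 3 as missing. For HV, average the three layer means. For the PsO CD3+ and Ki67 densities, use the sample's own field count as the denominator. Analyse change from baseline in these means with the existing ANCOVA and in SAP 13.

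Keep the common-minimum truncated sum as a sensitivity analysis, and tabulate the number of evaluable fields by treatment and visit so that any link between treatment and field availability can be seen.

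The cost is a one-line derivation change plus one repeat run. Results move to a per-field scale, so table units and the fixed priors in SAP 13 need checking on that scale. The downside is that short samples may read high if fields were ordered by density or depend on infiltrate, which the sensitivity analysis is there to show.

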10.1.2. Summary Measure

Absolute, change from baseline and percent change from baseline are of interest for HV and PsO.

Data will be available at baseline and Day 4 (for HV) or Day 29 (for PsO).

10.1.3. Population of Interest

The primary pharmacodynamics and biomarker analyses will be based on the Safety population, unless otherwise specified.

10.1.4. Statistical Methods

Details of the planned displays are provided in Appendix 9 and will be based on GSK data standards and statistical principles.

Unless otherwise specified, endpoints / variables defined in Section 10.1.1 will be summarised using descriptive statistics, graphically presented (where appropriate) and listed.

10.1.4.1. Statistical Methodology Specification

Endpoint / Variables

- Change from baseline in
 - LAG3+ (total cells averaged across 3 skin layers for HV and total cells in dermis and epidermis separately for PsO)
 - o CD3+:
 - total cells averaged across 3 skin layers for HV
 - cells per mm² in dermis and epidermis separately for PsO
- For epidermis only (PsO), change from baseline in
 - Ki67 (cells/mm)

Model Specification

- Endpoints will be statistically analysed using an ANCOVA model.
- Terms fitted in the model will include: Treatment and baseline

Model Results Presentation

- Summary table of the LS means and 95% CI for CFB (by treatment)
- [No plot as only 1 post-dose assessment]

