9. DATA ANALYSIS AND STATISTICAL CONSIDERATIONS

9.1. Hypotheses and Treatment Comparisons

The primary objective is to determine the safety and tolerability of single IV Doses of GSK2831781 in healthy volunteers and in patients with mild to moderate psoriasis.

There are no formal hypotheses planned.

An assessment of dose proportionality of AUC and Cmax, following single dosing, will be conducted separately for healthy volunteers and patients with psoriasis.

Where appropriate, an estimation approach will be used to address the study objectives where point estimates and corresponding confidence intervals will be constructed to provide a plausible range of values for the comparison of interest.

Exploratory comparisons will be conducted to investigate the effect of ADA status at baseline on the pharmacokinetics of GSK2831781.

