9.3.2.4. Pharmacodynamic/Biomarker Analyses

For Parts A and B, descriptive statistics, where appropriate, (n, arithmetic mean, geometric mean, standard deviation, minimum, median and maximum) will be calculated for the pharmacodynamic endpoints and the biomarkers and summarized by time for GSK2831781. Graphical displays will be produced over time if deemed appropriate. All data will be listed.

For Parts A and B, appropriate secondary pharmacodynamic/biomarker endpoints will be separately analysed using suitable mixed models repeated measures (MMRM) analysis, if deemed appropriate. Point estimates and their associated 95% confidence intervals will be constructed for the adjusted mean differences between "GSK2831781-placebo". Further details of the model terms (random and repeated effects), possible covariates and interactions between treatment and covariates will be included in the RAP.

Additional exploratory statistical analyses may also be performed to further characterise the pharmacodynamic/biomarker endpoints. Further details of the analyses will be provided in the RAP.

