2.2. Study Objectives and Endpoints

Objectives	End	lpoints
Primary	Primary	
To assess the safety and tolerability of single IV doses of GSK2831781 in healthy		Laboratory safety data (haematology, clinical chemistry, urinalysis)
volunteers and psoriasis patients.	•	Vital signs (blood pressure, heart rate, body temperature)
	•	12-lead ECGs
	•	Adverse events
	•	Inflammatory cytokine levels
Secondary Objectives		ondary Endpoints
To evaluate the pharmacology and clinical effect of a single IV dose of GSK2831781 in a DTH model in healthy volunteers.	•	Change from baseline (PPD 1st challenge) of induration diameter from re-challenge at 3 days post-dose Duration of induration in the re-challenge Change from baseline (PPD 1st challenge) of LAG-3+ cells in biopsies of re-challenged skin at 3 days post-dose, measured by IHC
To evaluate the pharmacology of a single IV dose of GSK2831781 in psoriasis patients.		Change from baseline in LAG-3+ cells in lesional biopsies at Day 29 measured by IHC
To evaluate the pharmacokinetics of single IV doses of GSK2831781 in healthy volunteers and psoriasis patients.		GSK2831781 PK parameters following single intravenous dose: AUC(0-∞), AUC(0-t), AUC(0-Week4), %AUCex, Cmax, tmax, tlast, CL, Vss, MRT, λz and t ½ when assessable
To evaluate the immunogenicity of GSK2831781 administered as a single IV dose in healthy volunteers and psoriasis patients.	•	Antibodies to GSK2831781 in serum
To evaluate the effect of a single IV dose of GSK2831781 on disease activity in psoriasis patients.	•	Change from baseline and actual PASI scores at Day 15, 29, 43, 85, 121 and follow-up
	•	Proportion of subjects who achieve ≥50% and ≥75% improvement from baseline in PASI score at Day 15, 29, 43, 85, 121 and follow-up (PASI 50 and PASI 75)
		Change from baseline and actual PLSS scores at Day 15, 29, 43, 85, 121 and follow-up
		Change from baseline and actual PGA scores at Day 15, 29, 43, 85 and 121
	•	Proportion of subjects in each PGA score category at Day 15, 29, 43, 85 and 121
	•	Proportion of subjects achieving PGA 0/1 and at least a 2-point improvement at Day 15, 29, 43, 85 and 121

Objectives	Endpoints		
Exploratory Objectives	Exploratory Endpoints		
To evaluate the effect of a single IV dose of GSK2831781 in psoriasis patients on biomarkers.	 Histopathological scoring of psoriatic lesional biopsies in subjects with psoriasis - Ki67, CD3 and epidermal thickness 		

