8.1.4.1. Statistical Methodology Specification

Endpoint

Change from baseline in induration diameter (mm) (Overall induration diameter only)

Model Specification

- Mixed models repeated measures (MMRM) model.
- Terms fitted in the MMRM model will include:
 - Fixed categorical covariates: Treatment, day (visit), treatment * day (visit) interaction
 - Fixed continuous covariates: Baseline (see Section 5.2 for baseline definition)
 - Repeated: Day (visit)
- An unstructured covariance will be used to account for the within-subject correlation. by specifying 'type=UN' on the REPEATED line.
- The Kenward and Roger method for approximating the denominator degrees of freedom and correcting for bias in the estimated variance-covariance of the fixed effects will be used.
- LSmeans of the CFB will be calculated using the observed margins (OM argument added in the LSmeans function)

Model Checking & Diagnostics

 In the event that this model fails to converge, alternative correlation structures may be considered.

Model Results Presentation

Table/Figure of the LS means and 95% CI (by treatment and visit)

Endpoint / Variables

Duration of induration of at least 6mm (days)

Model Specification

Hasard ratios will be estimated using the Pike estimator.

Model Results Presentation

- Summary table of the hazard ratios
- No plot

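### For DTH induration diameter and LAG-3+ cells the SAP asks for per-arm LS means only, omitting the active-minus-placebo difference with 95% CI that the protocol plans for modelled secondary endpoints

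*SAP*

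**What the plan says.** **Protocol.** Section 9.3.2.4, which covers Parts A and B, says that "appropriate secondary pharmacodynamic/biomarker endpoints will be separately analysed using suitable mixed models repeated measures (MMRM) analysis, if deemed appropriate". It continues: "Point estimates and their associated 95% confidence intervals will be constructed for the adjusted mean differences between" GSK2831781 and placebo. For anything further it says only that "Additional exploratory statistical analyses may also be performed to further characterise the pharmacodynamic/biomarker endpoints". The general statement in 9.1, which is also qualified, is that "point estimates and corresponding confidence intervals will be constructed to provide a plausible range of values for the comparison of interest".

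**Endpoint tiers (protocol section 2, SAP 2.2).** The secondary list includes "Change from baseline (PPD 1st challenge) of induration diameter from re-challenge at 3 days post-dose", LAG-3+ cells in the DTH biopsies, and LAG-3+ cells in psoriasis lesions at Day 29. Ki67, CD3 and epidermal thickness in psoriasis are exploratory.

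**SAP model output.**
- Induration diameter (8.1.4.1, MMRM): "Table/Figure of the LS means and 95% CI (by treatment and visit").
- LAG-3+, CD3+ and Ki67 (10.1.4.1, ANCOVA with treatment and baseline): "Summary table of the LS means and 95% CI for CFB (by treatment").
- Epidermal thickness (10.2.4.1, same ANCOVA): the same line as 10.1.4.1.
- PASI (8.3.4.1) and PLSS (8.4.4.1), both using the induration MMRM: LS means "as well as treatment differences and 95%CI".

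**Declared changes.** SAP Table 1 lists three departures from the protocol analysis: PK parameters, dose proportionality and soluble LAG-3. The between-arm differences are not mentioned.

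**The concern.** Induration diameter and LAG-3+ depletion are the secondary endpoints meant to show that the drug does what it was designed to do. The quantity that answers that question is the contrast with concurrent placebo. In the DTH cohort especially, the change from first challenge to re-challenge within one arm mixes any drug effect with whatever a second PPD challenge does by itself.

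The SAP fits models that contain this contrast but asks only for the arm means. It requests the difference for PASI and PLSS, where protocol 9.3.2.5 left formal analysis optional, and leaves it out where 9.3.2.4 planned it. If the outputs follow the text, readers are left to compare two separate intervals by eye, which is a poor substitute with about 6 subjects per arm.

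**Working it through.** The plan states no figure to reproduce here. The check has two parts: a comparison of the texts, and a calculation of how far the arm intervals fall short of the interval of the difference.

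**1. Which endpoints does the protocol sentence reach?**

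| Endpoint | Tier | Modelled in SAP | Difference with CI requested | Between-arm quantity in SAP section 13 |
|---|---|---|---|---|
| DTH induration diameter | Secondary | MMRM | No | None |
| LAG-3+, DTH biopsies | Secondary | ANCOVA | No | None |
| LAG-3+, psoriasis | Secondary | ANCOVA | No | Posterior probabilities, % change |
| CD3+, psoriasis | Exploratory | ANCOVA | No | None |
| Ki67, psoriasis | Exploratory | ANCOVA | No | Posterior probability |
| Epidermal thickness, psoriasis | Exploratory | ANCOVA | No | Posterior probability |
| PASI, PLSS | Secondary | MMRM | Yes | Posterior probabilities |

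CD3+ in the DTH biopsies is also modelled without a requested difference. It is not in the secondary list. Section 13 mainly pools 1.5 and 5 mg/kg against placebo; results for each of those two doses may also be calculated, and 0.5 mg/kg is not included. The listed outputs are probabilities, with no estimate and 95% interval.

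The undeclared departure from 9.3.2.4 therefore covers the first three rows only.

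**2. How far do arm intervals fall short?**

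The documents give no SD for these endpoints, so widths are in units of the residual SD. Assumptions: equal variance, balanced baseline, complete data.

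- Arm half-width = t × SD × √(1/n)
- Difference half-width = t × SD × √(1/n₁ + 1/n₂)
- Two arm intervals fail to overlap only when the difference exceeds the sum of the arm half-widths.

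*DTH cohort, 6 v 6.* Two arms plus a baseline slope give df = 12 − 3 = 9 and t = 2.262.
- Each arm: 2.262 × √(1/6) = 0.92 SD; the two sum to 1.85 SD.
- Difference: 2.262 × √(1/6 + 1/6) = 1.31 SD.
- Ratio: 1.85 / 1.31 = 1.41.

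*Psoriasis, one dose (6) v pooled placebo (9).* Four groups plus a baseline slope give df = 27 − 5 = 22 and t = 2.074.
- Active: 2.074 × √(1/6) = 0.85 SD. Placebo: 2.074 × √(1/9) = 0.69 SD. Sum: 1.54 SD.
- Difference: 2.074 × √(1/6 + 1/9) = 1.09 SD.
- Ratio: 1.54 / 1.09 = 1.41 (1.407 unrounded).

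Non-overlap at these sizes corresponds to a two-sided p of 0.011 for the difference at 9 df (t = 2.262 × 1.414) and 0.008 at 22 df (t = 2.074 × 1.407). For an assumed true difference of 2 SD at 6 v 6, the chance that the interval of the difference excludes zero is 87%, against 61% for non-overlap of the arm intervals. At 1.5 SD the figures are 64% and 34%. These show scale only.

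**The case against.** **The protocol wording is conditional.** It is, and that limits the point. But the condition attaches to whether a model is fitted. The SAP chose to fit one, and the sentence on differences then follows. Using ANCOVA rather than MMRM is natural with one post-dose biopsy and leaves the contrast available.

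**Induration is a clinical response, not a biomarker.** Protocol 6.5 and SAP section 8 do place it there, so LAG-3+ is the clearer case. Yet protocol 9.3.2.5 on efficacy covers Part B only, while 9.3.2.4 covers Parts A and B and names the kind of model that the SAP uses for induration.

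**There are other between-arm results.** Section 13 does give between-arm inference on psoriasis LAG-3+, Ki67 and epidermal thickness, and 8.1.4.1 plans a hazard ratio for duration of induration. Neither supplies an estimate with a 95% CI for the two endpoints at issue, and the DTH cohort has nothing for induration diameter or LAG-3+.

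**The difference may appear in the output anyway.** This is possible. Mock shells are not in the SAP, and raw SAS output is a planned listing. The notes to Tables 2.2, 6.4 and 6.5 do not exclude a difference, and the notes to Tables 2.7 and 2.9 do not mention one even though 8.3.4.1 and 8.4.4.1 require it. The point therefore rests on the results-presentation lines alone, which do not ask for the contrast.

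**Readings that go too far.** A reader might infer that the protocol requires these differences for every biopsy endpoint. It does not: the exploratory endpoints fall outside that sentence, so SAP Table 1 had nothing to declare for them. A reader might also infer that the trial yields no estimate of drug effect. The two LS means give the point difference; what is missing is its interval. Nor is there a 5% error rate being eroded: no formal hypotheses are planned, and nothing in the SAP says that overlap will be the criterion.

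**Conclusion.** The point holds for the secondary endpoints DTH induration diameter and LAG-3+ cells. Followed as written, the SAP produces no interval for the drug effect on either endpoint in the DTH cohort, and no 95% CI for the difference in psoriasis LAG-3+, although protocol 9.3.2.4 plans one for modelled secondary endpoints. The omission is not declared in SAP Table 1. For CD3+, Ki67 and epidermal thickness it is an inconsistency of presentation only.

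If readers fall back on overlap of arm intervals, they need a difference about 1.41 times as large as the interval of the difference would need. That factor depends on equal variance, balanced baseline and complete data, and it describes an informal habit of reading rather than a planned test. Sample size, data and error control are unaffected.

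**What to change.** - In SAP 8.1.4.1 and 10.1.4.1, add treatment differences (each dose minus placebo) with 95% CI from the models already specified, in line with 8.3.4.1 and 8.4.4.1.
- State the same in the notes to Tables 2.2, 6.4 and 6.5. For induration, show the difference at the reading 3 days post-dose, which is the secondary endpoint; the treatment-by-visit term already allows it.
- For CD3+, Ki67 and epidermal thickness (10.1.4.1, 10.2.4.1), add the same line for consistency.
- If the sponsor prefers to leave the differences out for induration and LAG-3+, declare and justify that in SAP Table 1.

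The cost is one contrast statement per existing model, with no new data and no change to sample size. SAP 14.9.3 already provides for a review of which outputs to re-run at the final analysis, which is a natural place to make the addition.
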